### 3. EXPECTED RISK AND BENEFITS

#### Potential risks:

• Skin irritation from allergic reactions to sesame oil or liquid paraffin oil

#### Potential benefits:

- Reduced risk in developing phlebitis at the IV cannula site due to the topical application of sesame oil. (direct)
- Gained knowledge with regards to phlebitis risk factors, signs and symptoms and consequences. (Indirect)

#### 4. STUDY POPULATION

#### 4.1. List the number and nature of subjects to be enrolled.

650 adult patients between the age of 21 to 80, and from inpatient wards within The National Heart Centre of Singapore will be recruited, regardless of ethnicity or gender.

#### 4.2. Criteria for Recruitment and Recruitment Process

All newly admitted patients with an existing IV cannula will be approached after being admitted into an inpatient ward. This will take place within 12 hours of the IV cannula insertion. They will not be approached if in distress, drowsy or immediately prior to a surgical procedure. The IV cannula will be tested for patency, and assessed for redness, swelling, pain, a palpable venous cord or pyrexia. If any of these symptoms are present, or if the IV cannula is not patent, the recruitment will be terminated.

#### 4.3. Inclusion Criteria

- Age 21-80
- Patients must speak and understand either English or Mandarin
- Patients who possess a peripheral IV cannula
- IV cannula must have been inserted for less than 12 hours
- IV cannula must be on an upper extremity
- IV cannula must be patent
- IV cannula sites must show no signs of redness, swelling, pain, a palpable venous cord or pyrexia
- Patient must be admitted to a cardiology ward in the National Heart Centre Singapore

#### 4.4. Exclusion Criteria

- Patients who do not speak or understand either English or Mandarin
- Patients with venous insufficiency
- Patients with coagulopathies
- Patients with cognitive or sensory impairments that would inhibit their ability to rate their pain via a Numerical Rating Scale (NRS)
- Patients who are receiving medications that might interfere with timely reporting of adverse events (eg. medications that cause severe drowsiness)
- Patients who report allergies to sesame or liquid paraffin oil
- IV cannulas that were inserted and used for resuscitation
- Patients with existing skin conditions that cause their skin to be red or swollen and might affect the investigators ability to assess for phlebitis
- Patients who possess more than one peripheral IV cannula will only be included in the study once. All subsequent IV cannula insertions will be excluded.

#### 5. STUDY DESIGN AND PROCEDURES/METHODOLOGY

A physical copy of the informed consent form will be provided to the inpatient wards included in the study. Ward staff will also be briefed verbally on the research details, data collection methods and safety information of the study.

Ward nurses will notify investigators, of any patient who has been admitted to the ward

with an existing IV cannula, or has had a new IV cannula set in the last 12 hours. The investigators will review the patient's medical history to assess for venous insufficiencies, coagulation disorders, cognitive or sensory impairments, and medications that might interfere with the timely reporting of adverse events. Patients will be approached after being admitted into an inpatient ward, within 12 hours of the IV cannula insertion. They will not be approached if in distress, drowsy or immediately prior to a surgical procedure. The investigator will access the patency of the peripheral IV cannula, and the IV cannula site for signs of redness, swelling, pain, a palpable venous cord or pyrexia. If the patient meets the criteria for inclusion, informed consent will be taken at the patient's bedside, in the presence of a witness, with drawn curtains to maintain privacy, reduce distractions and prevent undue influence from other individuals within the ward. The participant will be given time to consider their participation before giving their response to the investigator at the bedside. If they require more time for consideration, the investigator will leave the bedside and contact them again within 12 hours of IV cannula insertion to confirm recruitment. The investigator will emphasise the patient's right to make their own decision with regards to participating in the study. All details of the study and risks and benefits will be provided without any pressure on the patient to be recruited.

The patient will then be randomly allocated to the experimental or control group with the use of a randomisation software (MS excel). 5 drops/0.25mls of 100% sesame oil or mineral oil will be applied to the IV cannula site, from 3cm above the insertion point to 10cm along the vein, with a width of 2cm on either side (Appendix A). There will be no massaging or manipulation of the infusion site during application.

Demographic and clinical data will be recorded into a table. The patient will be instructed not to wash or wipe the topical agent off. The time and date of the start of treatment applied and subsequent treatments at 12 hour intervals will be documented. At the start of the study and at each 12 hour interval, the investigator will observe for signs of phlebitis using the Visual Infusion Phlebitis scoring tool [Appendix 2], before application of the next treatment. The study investigators will be the only ones applying the treatment/control and completing the data collection form [Appendix 3] every 12 hours. Patient identifiers (name and NRIC) will be verified before every application of the treatment/control and the completion of the data collection form.

Application of the treatment or control will be made every 12 hours for up to 72 hours, where the IV cannula will then be removed according to hospital guidelines. The IV cannula site will be observed, every 12 hours for up to 24 hours post IV cannula removal, for phlebitis or complications.

Patients will be withdrawn from the study the moment they show signs of adverse reactions from the topical treatment or control.

Participants will be involved in the study for a maximum of 96 hours. If the IV cannula is removed accidentally or not due to phlebitis before the 72-hour period is up, re-insertion of a new cannula and re-application of oils will not be done on a new site. The patient's IV cannula site will continue to be observed for 24 hours at 12-hour intervals after cannula removal. The partial data will be kept and analysed. If the patient is discharged before the 96 hour observation period is up, the 24 hour post-removal observation will continue to be carried out at 12 hour intervals, via phone call or video call. The patients' phone numbers will be obtained during the informed consent process, only for follow up purposes.

The application of either sesame oil or liquid paraffin oil is not part of the routine procedures or standard of care in the ward, and will only be applied for the purpose of this research. Both the sesame oil and liquid paraffin oil are marketed products and will be used as per label.

The study is estimated to continue for two years, commencing in February 2022 and ending in December 2023.

At no point of the study will any audio or video recording take place.

All hardcopy research data will be stored in in a locked cupboard with lock and key access within the National Heart Centre, Singapore. All soft copies will be stored in a password protected Laptop belonging to the principal investigator. Only the principal investigator will have access to the research data. All other members of the research team will access the data through the principal investigator. The physical research data will be kept under lock and key for 7 years after the completion of the research study or date of publication of the research using the research data, whichever is later. After which, all data will be destroyed. Hardcopies will be shredded and soft copies will be deleted.

Subjects may withdraw voluntarily from participation in the study at any time. Subjects may also withdraw voluntarily from receiving the study intervention for any reason. Upon withdrawal, IV cannula sites will continue to be observed for 24 hours at 12-hour intervals for potential reactions to the oils or signs of phlebitis. If there are any adverse reactions to the oils or signs of phlebitis during the 24-hour observation period, the patient will be referred to the attending physician and medical treatment will be rendered. The patient will continue to receive follow-up and medical treatment until symptoms have resolved.

The study may be discontinued at any time, if safety issues arise. If the risks to participants unexpectedly outweigh the benefits due to unexpected severe adverse events due to the application of the treatment or control oils, the study may then be suspended until the risk-benefit ratio is re-evaluated.

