#### 7. DATA ANALYSIS

#### 7.1. Data Quality Assurance

Study investigators will be the only ones applying the treatment/control and completing the data collection form every 12 hours. Patient identifiers (name and NRIC) will be verified before every application of the treatment/control and the completion of the data collection form. The principal investigator will perform weekly checks and random audits to ensure that all informed consent forms and data collection forms are completed accurately.

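### No masking is described: the investigators both apply the named oils and score phlebitis, so a small to moderate difference could partly reflect expectation

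*Combined protocol and SAP*

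**What the plan says.** Section 5 makes one group responsible for both treatment and outcome: "The study investigators will be the only ones applying the treatment/control and completing the data collection form [Appendix 3] every 12 hours". Section 7.1 repeats this as a data quality measure: "Study investigators will be the only ones applying the treatment/control and completing the data collection form every 12 hours". The products are identified by name: "5 drops/0.25mls of 100% sesame oil or mineral oil will be applied to the IV cannula site". Allocation follows consent and is made with MS Excel. Section 5 does not say who holds the list or whether the next assignment is hidden.

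VIP is scored at the start and every 12 hours, "before application of the next treatment". Between visits the oil stays on the skin: "The patient will be instructed not to wash or wipe the topical agent off". For patients discharged early, the observation after removal "will continue to be carried out at 12 hour intervals, via phone call or video call".

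In the scoring tool (Appendix 2), grade 1 needs slight pain or slight redness. Grade 2 needs any two of pain, redness and swelling, so pain with redness is enough. Swelling becomes compulsory at grade 3, a palpable cord at grade 4 and pyrexia at grade 5. The text does not say which grade counts as phlebitis. The only comparative objective in Section 2, incidence and severity by oil, rests on this score.

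**The concern.** A scorer who knows the oil and expects it to work may read faint redness or mild tenderness differently in the two arms. The expectation is on record: the Background closes by stating a belief that sesame oil is effective, and Section 3 lists a lower risk of phlebitis from sesame oil as a direct benefit. Patients are told the risks and benefits, and pain presumably comes from their own report, so the same applies to them. Masking of participants is not described either.

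The outcome is most open to judgement at its lowest grades, and these may count as events. Bias in scoring cannot be removed at analysis. The identifier checks, weekly reviews and audits in Sections 7.1 and 10 address accuracy and completeness. The baseline comparison and selection-bias tests in Section 8.2 cannot detect differential scoring. What is at stake is whether a modest observed benefit could be credited to the oil.

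**Working it through.** **Figures in the plan.** None bears on masking, so there is nothing to reproduce first. The check asks how much a given scoring shift would matter at the sizes the plan states.

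**Inputs from the documents**
- Enrolment: 650 (Section 4.1) and 100 (Section 8.1). The two conflict, which is a separate matter, so both are shown.
- Attrition: 5% (Section 8.1, given for the figure of 100).
- Phlebitis incidence: 5 to 75% (Background).
- Design difference: 35% (Section 8.1), read as percentage points.

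**Assumptions**
- A yes/no endpoint, a 1:1 split and a two-sided 5% test.
- The 5% attrition applied to 650 as well as to 100.
- Incidence p of 20, 30, 50 or 75%. Lower values within the cited range are not shown.
- A scoring shift s in favour of sesame oil. No document gives one.

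**Patients per arm.** 650 × 0.95 / 2 = 308.75, taken as 308. 100 × 0.95 / 2 = 47.5, taken as 47.

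**Rejection probability with no true effect.** Control is scored at p and sesame at q = p − s. With m = (p + q)/2, SE0 = √(2m(1 − m)/n) and SE1 = √((p(1 − p) + q(1 − q))/n):

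P(reject) = Φ((s − 1.96·SE0)/SE1) + Φ((−s − 1.96·SE0)/SE1)

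Example with p = 0.30, s = 0.05:
- n = 308: SE0 = 0.0360, SE1 = 0.0359. (0.05 − 0.0705)/0.0359 = −0.57, giving 0.284. The other tail is negligible.
- n = 47: SE0 = 0.0921, SE1 = 0.0920. (0.05 − 0.1805)/0.0920 = −1.42, giving 0.078. The other tail adds 0.006, for a total of 0.084.

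Results for a 5-point shift:

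| Incidence | Share of events removed | 308 per arm, normal / exact | 47 per arm, normal / exact |
|---|---|---|---|
| 20% | 25% | 0.372 / 0.373 | 0.097 / 0.102 |
| 30% | 17% | 0.284 / 0.285 | 0.084 / 0.085 |
| 50% | 10% | 0.237 / 0.232 | 0.077 / 0.076 |
| 75% | 7% | 0.284 / 0.285 | 0.084 / 0.085 |

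The exact column enumerates both binomial distributions and applies the same test. With no shift the exact rejection rate is 0.048–0.051. By the normal approximation, a 2-point shift gives 8–10% at 308 per arm and 5–6% at 47.

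**Smallest observed gap that reaches significance**, 1.96·√(2p(1 − p)/n): 6–8 points at 308 per arm and 16–20 points at 47.

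**Could a shift produce 35 points?** Exact probability of an observed gap of at least 35 points at 47 per arm, with no true effect:
- 8-point shift: 0.0002 to 0.0037 over the four incidences.
- 20-point shift: about 6% at incidence 50% or 75%.
- 25-point shift: about 15% at incidence 50% or 75%.

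Alternatively, suppose a share k of sesame events is scored down and the same share of control non-events is scored up. The apparent gap is kp + k(1 − p) = k, so an expected gap of 35 points needs about 35% misscoring in each direction.

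**The case against.** The strongest reply is that lack of description is not exposure. Title and front pages were not part of the text reviewed, and a masking statement there cannot be excluded. The comparator is another oil although neither oil is standard care, which fits an intended but unreported mask. A reader might infer that the trial is open-label, or that one person applies and scores for each patient. The documents support neither: they name the investigators as a group and do not say what a scorer knows. Nor does the application row on the data collection form prove that the arm is visible. The tick may record only that oil was applied, and the form header shows a participant number and no arm. Foreseeable allocation is possible, since the holder of the Excel list is not named, but it is not shown.

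Scoring before the next application helps little, because it does not mask an investigator who knows the oil from earlier visits.

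The illustration also rests on an assumed shift. At 100 patients, the only size that Section 8.1 arrives at, rejection rises only from about 5% to 8–10%. Both objections stand as limits on size and certainty. Neither supplies a masking step in Section 5, where such a step would belong.

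**Conclusion.** The point holds as a gap in the design as written, and should be corrected. It is modest at 100 patients and larger at 650. With no true effect and an assumed 5-point shift, rejection is about 8–10% at 47 per arm and 23–37% at 308, under the assumptions listed above. It concerns small to moderate differences, which could partly reflect expectation.

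Two stronger readings should be avoided. One is that a 35-point result would be an artefact of scoring: this is a less plausible explanation, needing heavy misscoring. The other is that a 35-point result would be immune. That rests on capping the shift at 8 points; a 20-point shift yields such a gap about 6% of the time at 47 per arm and incidence 50–75%. Scoring bias is therefore not excluded even there.

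Confidence is medium, because masking may be intended but unstated.

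**What to change.** In Section 5:

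1. Dispense both oils in identical, opaque, participant-numbered bottles, opened in sequence after consent.
2. Have the allocation list generated in advance and held by a team member who neither enrols nor scores, if the existing team has one. The documents do not show whether it does.
3. Reword the form's application row so that it records only that study oil was applied.
4. Keep the code closed until database lock, except for adverse reactions.

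A scorer who did not make that patient's earlier applications is optional, and only where it needs no extra staff. If masking is already planned, state it in Section 5. If it is not feasible, say so and report it as a limitation.

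**Cost.** One small bottle and label per participant, packing time and one form edit. At 0.25 ml per application and 6 to 7 applications over 72 hours, each bottle holds 1.5 to 1.75 ml. Bottle prices are not given. The grant of $20,090 (Section 14) is about $201 per participant at 100 (20,090/100) and $31 at 650 (20,090/650), so the cost needs checking at the larger size. Repackaging must be checked against the statement that "Both the sesame oil and liquid paraffin oil are marketed products and will be used as per label". Masking may be only partial, because smell, colour or oil left on the skin may reveal the arm even to a different scorer. That should be reported as a limitation.

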#### 6. SAFETY MEASUREMENTS

#### 6.1. Definitions

Serious adverse event (SAE) in relation to human biomedical research, means any untoward medical occurrence as a result of any human biomedical research which:

- results in or contributes to death
- is life-threatening
- requires in-patient hospitalisation or prolongation of existing hospitalisation
- results in or contributes to persistent or significant disability/incapacity or
- results in or contributes to a congenital anomaly/birth defect
- results in such other events as may be prescribed

Adverse event (AE) in relation to human biomedical research means any untoward medical occurrence as a result of any human biomedical research which is NOT serious. Adverse event can be any unfavourable and unintended sign (including an abnormal laboratory finding), symptom, or disease possibly/ probably/ definitely associated with the participant in the human biomedical research.

#### 6.2. Collecting, Recording and Reporting of Serious Adverse Events (SAEs) to CIRB

Only related SAEs (definitely/ probably/ possibly) will be reported to CIRB. Related means there is a reasonable possibility that the event may have been caused by participation in the research. Please refer to the CIRB website for more information on Reporting Requirement and Timeline for Serious Adverse Events.

The investigator is responsible for informing CIRB after first knowledge that the case qualifies for reporting. Follow-up information will be actively sought and submitted as it becomes available.

Related AEs will not be reported to CIRB. However, the investigator is responsible to keep record of such AEs cases at the Study Site File.

#### 6.3. Safety Monitoring Plan

All participants will have their IV cannula sites monitored for adverse reactions to the application of the treatment or control oils, and for signs of phlebitis every 12 hours. Participants will also be educated on the signs of allergies or sensitivities to the oils, and the signs of phlebitis. They will be advised to contact the investigators immediately upon detection of adverse reactions or phlebitis. The moment they experience any adverse reactions to the topical oils, they will be withdrawn from the study. A referral will be made to the attending physician in the ward, and treatment will be rendered. The participant will continue to receive follow up, observations and treatment until the reactions or symptoms resolve.

All hardcopy research data will be stored in in a locked cupboard with lock and key access within the National Heart Centre, Singapore. All soft copies will be stored in a password protected Laptop belonging to the principal investigator. Only the principal investigator will have access to the research data. All other members of the research team will access the data through the principal investigator. The physical research data will be kept under lock and key for 7 years after the completion of the research study or date of publication of the research using the research data, whichever is later. After which, all data will be destroyed. Hardcopies will be shredded and soft copies will be deleted.

### 6.4. Complaint Handling

The investigators in the study will respond to and try to resolve any study-related concern or complaint that is received. If a significant complaint or concern arises, in that a participant's safety, rights or welfare may be severely impacted, it will be reported to the Singhealth Centralised Institutional Review Board (IRB).

#### 7. DATA ANALYSIS

#### 7.1. Data Quality Assurance

Study investigators will be the only ones applying the treatment/control and completing the data collection form every 12 hours. Patient identifiers (name and NRIC) will be verified before every application of the treatment/control and the completion of the data collection form. The principal investigator will perform weekly checks and random audits to ensure that all informed consent forms and data collection forms are completed accurately.

#### 7.2. Data Entry and Storage

Informed consent forms will be on paper. Data will be both on paper, and entered and stored electronically. The physical research data will be kept under lock and key for 7 years after the completion of the research study or date of publication of the research using the research data, whichever is later. After which, all data will be destroyed. Hardcopies will be shredded and soft copies will be deleted.

### 8. SAMPLE SIZE AND STATISTICAL METHODS

#### 8.1. Determination of Sample Size

Using a power analysis of 20% and a difference of 35%, a sample size of 44 participants is required if subgroup analysis is not required. We then rounded it up to 100 to account for an attrition rate of 5%.

Data will be analysed with the Statistical Package for Social Science (SPSS) software program (v. 28) using descriptive statistics such as relative and absolute frequencies, mean and standard deviation, and inferential statistics such as Chi-square, independent t-test and Hazard ratio.

#### 8.2. Statistical and Analytical Plans

#### a. General Considerations

The distribution and dispersion of the data will be examined through descriptive numerical summaries and graphical tools such as scatter plots, via SPSS. The data will then be analysed using descriptive statistics such as relative and absolute frequencies, mean and standard deviation, and inferential statistics such as Chi-square, independent t-test and Hazard ratio.

As missing data can potentially spoil or invalidate a study, we will spare no effort in minimising incomplete or missing data. All data will be carefully inspected to identify missing items and outliers. In the analysis of incomplete data, we will consult with a biostatistician regarding the use of incomplete-data analysis strategies that will allow us to utilise the available information effectively.

b. Safety Analyses

All adverse events, such as the development of allergic reactions to the oils, leading to the participant's withdrawal from the study will be collected and tabulated. Incidences and severity of phlebitis experienced during the course of the study will also be collected and tabulated. All adverse reactions and phlebitis incidences will be tabulated for both the treatment and control group. The extent and severity of symptoms will also be documented. For phlebitis incidences, the severity will be assessed with the Visual Infusion Phlebitis (VIP) scoring tool [Appendix 2]. The number of adverse reactions will be summarised for both the treatment and control group. Frequency counts and percentages will be calculated and reported.

c. Interim Analyses

We will compare treatment groups on descriptive and clinical characteristics at baseline to ensure that randomisation has succeeded. SPSS will be used for group comparisons, descriptive calculations and conditional regression modelling. We will examine the distributions of all important variables at baseline and at the end of the data collection period, to assess for covariate imbalance. Formal statistical methods to test for selection bias will be used.

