### 1. BACKGROUND AND RATIONALE

The insertion of peripheral intravenous (IV) cannulas for the administration of medications, fluid and blood products is commonplace in hospitals today (1). Peripheral IV cannulas are minimally invasive and offer physicians and nurses the convenience of administering IV therapy as necessary (2). However, despite the many therapeutic benefits that IV cannulas offer, they can lead to complications such as infiltration, extravasation, bleeding, bruising, infection and phlebitis (2, 3). Of all the aforementioned complications, phlebitis is one of the most common and has been found to affect 5 to 75% of patients undergoing IV therapy in hospitals (4, 5).

Phlebitis refers to the inflammation of the venous tract and its surrounding tissues (5, 6). It can be caused by mechanical trauma, chemical irritation or infectious microorganisms (5, 7). Mechanical phlebitis results when the inserted IV cannula moves within the vein, causing friction and subsequently inflammation (8). Chemical phlebitis is caused by solutions that are hypertonic (osmolality > 500mOsm/litre) or are too acidic or alkali in nature (pH < 5 or pH > 9) (9). Infective phlebitis results when bacteria penetrate the vein, from the time of insertion or the initiation of IV therapy, and colonise the site, leading to inflammation and in serious cases, systemic sepsis (10).

The signs and symptoms associated with phlebitis include varying degrees of one or more of the following: erythema, pain, oedema, warmth, palpable venous cords, and purulent drainage (4). Using the VIP scale as modified by Jackson (4), the phlebitis grading can range from 0, indicating no signs of phlebitis, to 5, with symptoms of redness, pyrexia, a palpable venous cord and purulent drainage (4).

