# **Data Collection Form**

IV plug assessment	Insertion Date		Day 1 Date		Day 2 Date		Day 3 (Removal) Date		Post Removal
									Date
	0 hrs	12 hrs	24 hrs	36 hrs	48 hrs	60hrs	72hrs (Removal)	12 hrs post removal	24 hrs post removal
VIP Score (0-5)									
Treatment/ Control applied (Please tick)									
Current drug infusion									
Other drugs administered via this IV Cannula in the past 12hrs									
Initials

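### Cannula-site complications are recorded only in part and no comparison of them by arm is planned: adverse events are limited to those attributed to the research, and the 12-hourly grid has no complication row

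*Combined protocol and SAP*

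**What the plan says.** Section 1 (Background and Rationale) says of peripheral cannulas that "they can lead to complications such as infiltration, extravasation, bleeding, bruising, infection and phlebitis". Section 5 asks for the site to be observed after removal, every 12 hours for up to 24 hours, for complications as well as phlebitis. It also foresees removal by accident, or for a reason other than phlebitis, before 72 hours. The site is then followed for a further 24 hours, and the partial data are kept and analysed.

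Section 6.1 builds attribution into the definition. An adverse event is "any untoward medical occurrence as a result of any human biomedical research which is NOT serious", and the same clause runs on to a "disease possibly/ probably/ definitely associated with the participant in the human biomedical research". The definition of a serious adverse event carries the same causal condition. Section 6.2 states: "Only related SAEs (definitely/ probably/ possibly) will be reported to CIRB". For related non-serious events, "the investigator is responsible to keep record of such AEs cases at the Study Site File". It gives no rule for recording an event judged unrelated. Section 6.3 directs the 12-hourly monitoring at reactions to the oils and signs of phlebitis.

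Section 8.2b says that adverse events "leading to the participant's withdrawal from the study will be collected and tabulated". It then plans to tabulate all adverse reactions and all phlebitis for both groups.

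The 12-hourly grid has five rows: VIP score, a tick for treatment or control, current infusion, "Other drugs administered via this IV Cannula in the past 12hrs", and initials. The header of the form also has insertion date and time, and removal date, time and reason.

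**The concern.** In a randomised trial the comparison between arms tells us whether an intervention causes an event. Asking the investigator first whether each event was caused by the oil, and keeping only those judged at least possibly related, removes information that randomisation would have supplied without that judgement. Oil is placed around the insertion site every 12 hours, so whether it affects the security of the cannula or the state of the site is a reasonable question for this trial.

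There is also a link to efficacy. Early removal ends application and shortens the time in which phlebitis can be seen. If early removal differed between arms, the arm that lost cannulas sooner would have less opportunity to show phlebitis. A reader of the results would want dwell time and reasons for removal by arm in order to judge this, and the plan does not call for either.

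**Working it through.** The plan gives no figure on this point and no complication rates, so the check sets the sections side by side and asks, for each kind of event, where it is recorded and whether 8.2b summarises it by arm.

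| Event | Where it would be recorded | Summary by arm planned |
|---|---|---|
| Phlebitis | VIP row of the grid | Yes |
| Skin reaction attributed to an oil | Study Site File (6.2); no grid row | Yes, as an adverse reaction |
| Accidental dislodgement, or a complication that ended the cannula | Removal reason in the header, free text | No |
| Dwell time | Derivable from the header | No |
| Complication that did not end the cannula, judged unrelated | No field of its own | No |
| Complication arising after removal, judged unrelated | No field of its own | No |

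**Dwell time.** Dwell time = removal date and time − insertion date and time. All the inputs are in the header, so nothing new need be collected.

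**Named complications.** Section 1 lists six complications. Without phlebitis, 6 − 1 = 5 remain: infiltration, extravasation, bleeding, bruising and infection. None has a row on the grid.

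**What the VIP row picks up.** The modified tool scores signs whatever their cause. A site with two of pain, redness and swelling scores 2, so an infiltration that shows two of these would be counted as phlebitis. Grade 1 needs slight pain or slight redness, so swelling alone, or a bruise or bleed without pain or redness, does not reach it. Pyrexia enters only at grade 5, together with all the other listed signs. Coverage of the five is therefore partial, and what is covered carries the label phlebitis.

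**Observation time.** As an illustration, take a cannula lost at 30 hours on the grid's clock. Observation ends at 30 + 24 = 54 hours, against 72 + 24 = 96 hours for a cannula that stays the full course: 96 − 54 = 42 hours less. The plan keeps these data, but does not say that such losses will be shown by arm.

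**The case against.** The strongest reply is that targeted safety collection is a legitimate choice for two marketed topical oils, and that the documents capture more than they first appear to.

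- **Low threshold.** Attribution extends to events possibly related, and 6.2 defines related as a reasonable possibility. This stands: many site events could qualify. It still leaves the decision to case-by-case judgement.
- **Other records exist.** Section 6.2 keeps related events in the Study Site File, so the missing grid row does not mean that skin reactions go unrecorded. This stands. The weakness is that the file is not a structured record at each 12-hour check.
- **Withdrawal.** A reader might infer from the opening of 8.2b that only events leading to withdrawal are tabulated. The text does not support that. It goes on to tabulate all adverse reactions by group, and sections 5 and 6.3 withdraw every participant who reacts to an oil.
- **The form.** A reader might infer that the form has nowhere to record dislodgement or a complication that ends the cannula. The header's removal reason is such a place.
- **Accidental removal.** A reader might infer that these participants drop out of the analysis. Section 5 says the opposite.
- **Time at risk.** Sections 8.1 and 8.2a list a hazard ratio, which can allow for differing time under observation, and 8.2c looks at the distribution of important variables at the end of data collection. This answers part of the efficacy worry. However, a hazard ratio does not display how many cannulas were lost or why, and 8.2c concerns covariate imbalance and names neither dwell time nor removal reason.

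**Conclusion.** The point holds in a limited form. As written, the plan makes recording of site complications depend on attribution, gives them no row on the 12-hourly grid, and plans summaries by arm only for adverse reactions and phlebitis. Removal reason and dwell time can be recovered from the header but have no planned summary. Complications that did not end the cannula, or that came after removal, have no field of their own, except where their signs score on the VIP tool.

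A reader might go further and infer that the arms cannot be compared on complications at all, or that a benefit on phlebitis would be false. Neither follows. No comparison is planned, but for events that ended the cannula one could still be made from the header. Nothing in the documents suggests that either oil loosens cannulas.

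No numerical size is given. Any power calculation would need assumed complication rates and an assumed fraction attributed to the oil, and the safety analysis is descriptive in any case. The conclusion assumes that sections 6.1 to 6.3 are followed as written and that the form shown is the one used. It is a worthwhile, low-cost improvement and does not undermine the main comparison. Complications not noted at the bedside may be hard to reconstruct later.

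**What to change.** - **Form.** Add one tick-row to the 12-hourly grid for site complications (infiltration, extravasation, bleeding, bruising, infection) and skin reactions, completed whatever the attribution, with relatedness as a separate field. The grid has nine columns (seven from 0 to 72 hours and two after removal), so this is at most nine ticks per participant.
- **Removal reason.** Replace the free text with a short coded list that includes accidental dislodgement, phlebitis, each named complication, scheduled removal and other.
- **Sections 6.2 and 6.3.** Add a sentence saying that site complications are recorded at each check regardless of attribution. Reporting to the CIRB can stay limited to related serious adverse events.
- **Section 8.2b.** Plan one table, by randomised arm, of site complications, reason for removal and dwell time.

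The cost is one row, one code list, a short text change and one table. No visits are added, because the site is already checked every 12 hours. The small downside is that some events unrelated to the oils will be recorded.
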